9.5 Procedure for Accounting for Missing, Unused, and Spurious Data (if applicable)

In the ITT population, to perform the statistical analyses that uses the end point (the last time-point of each variable), if a subject prematurely withdraws from the study, missing data with respect to each variable will be replaced by the mean value of the corresponding treatment group at the corresponding visit.

9.6 Reporting Deviation(s) from the Statistical Analysis Plan

The detailed statistical analysis methodologies will be documented in the Statistical Analysis Plan. If there are any deviations from the originally planned analyses in the Statistical Analysis Plan, they will be fully described and justified in the protocol amendment(s) and/or final Clinical Study Report.

9.7 Subject Population(s) for Analysis

The Safety population consists of all subjects who received any amount of study drug.

The Intent-to-treat (ITT) population consists of all subjects randomized who received at least one dose of study medication for whom at least one post-baseline anti-A β 40 antibody signal assessment is available.

There will be two per-protocol (PP) populations:

- Part A: consists of all subjects who have received all doses of study medication (on V1, V4, V7, V10, V13 and V18), have attended the safety visit after booster (V20) and have no major protocol deviations.
- Part B: consist of all subjects who have received all doses of study medication (on V1B, V4B, V7B, V10B, V13B and V18B), have attended the safety visit after booster (V20B) and have no major protocol deviations.

10 DIRECT ACCESS TO SOURCE DATA/DOCUMENTS

The data will be recorded and kept current in eCRFs (and corresponding source documents) by the study site personnel directly responsible for the information and reviewed for completeness by the monitor. Araclon-Grifols personnel or designee can review the records.

In accordance with ICH GCP guidelines, the monitor must have direct access to the investigator's source documentation in order to verify the data recorded in the eCRFs for consistency and to verify adherence to the protocol, and the completeness, consistency, and accuracy of data entered. "Source documentation" includes individual subject files, separate from the eCRFs, which should be maintained and include visit dates, laboratory results, concomitant treatment, vital signs, medical history, examinations, AEs, investigational product dispensing logs, and other notes as appropriate. The investigator agrees to cooperate with the monitor to ensure that any problems noted during the course of these monitoring visits are resolved.

The investigator agrees to allow an auditor appointed by the sponsor as well as representatives of the relevant authorities and the ethics committees to verify, through an audit at the study center, that the study is implemented and documented according to the study protocol, good clinical practice and applicable regulations. The auditor/inspector will have to examine all essential documents and verify from a random sample of data entered into the clinical report forms is correct according to the original data found in clinical records. Therefore, the researcher will provide direct access to the data/documents and locations where trial activities are carried out (e.g., Laboratories, rooms and hospital pharmacy).

11 QUALITY CONTROL AND QUALITY ASSURANCE

Monitoring and auditing procedures defined/agreed by the sponsor will be followed, in order to comply with ICH GCP guidelines. Each center will be visited at regular intervals by a monitor to ensure compliance with the study protocol, ICH GCP and legal aspects. The on-site verification of the eCRF for completeness and clarity will include cross checking with source documents, and clarification of administrative matters. Query verification of data will be described in the Data Management Plan.

Representatives of regulatory authorities or of Araclon-Grifols may conduct audits or inspections or audits of the investigator study site. If the investigator is notified of an audit or inspection by a regulatory authority, the investigator agrees to notify the Araclon-Grifols Representative (eg, CAM, PM, PL) immediately. The investigator agrees to provide to representatives of a Regulatory Agency or Araclon-Grifols access to records, facilities, and personnel for the effective conduct of an audit or inspection.

11.1 Monitoring

This study will be monitored regularly by a clinical monitor according to the GCP guidelines of the ICH and appropriate standard operating procedures (SOPs).

Before the study begins, the monitor will review the protocol and eCRFs with the researcher and his team.

It is the investigator's responsibility to ensure that the study is carried out according to the agreed study protocol and that data sent to the sponsor in the eCRF and in all required reports are accurate, complete, legible and on time. Furthermore, it is the investigator's responsibility to ensure that all relevant data such as the patient's medical history, concomitant diseases and medication, date of inclusion in the study, dates of study visits, results of examinations and development if adverse events are documented correctly in the subject's original files.

The investigator will be responsible for making sure that all persons involved in the trial receive training regarding their duties.

The investigator agrees to allow the monitor to personally verify the correct execution and documentation of the study during scheduled visits. The purpose of trial monitoring is to verify that:

- The human rights and welfare are protected.
- The data reported are accurate, complete, and verifiable from original documents.
- The conduct of the trial is consistent with the up-to-date approved protocol and any possible amendments, with GCP and with applicable legal requirements.

To this end, data entered in the eCRF will be compared with data from medical records, etc. In particular, the availability of signed and dated informed consent will be checked. No information from the medical records regarding the identity of the subjects in the study will leave the study center.

For the verification of the original data, as a minimum the following information from patient files will be included:

- Date of patient written informed consent, selection number of,
- Dates of patient visits, adverse events (mild and severe),
- Confirmation of the diagnosis of the indication that is being treated (mild or moderate AD in this case),
- IMP and administration regimen (e.g., Initiation of treatment, dose), concomitant medication,
- Primary variables of biological activity, secondary variables of biological activity.

Print outs of the analytic data, EKGs and MRI data are considered original data.

The investigator and their team will cooperate with the clinical monitor, providing any missing information whenever possible. The investigator will be available to answer any questions that arise during monitoring of the study.

11.2 Audit and inspection

The investigator agrees to allow an auditor appointed by the sponsor as well as representatives of the relevant authorities and the ethics committees to verify, through an audit at the study center, that the study is implemented and documented according to the study protocol, good clinical practice and applicable regulations. The auditor/inspector will have to examine all essential documents and verify from a random sample of data entered into the clinical report forms is correct according to the original data found in clinical records. Therefore, the researcher will provide direct access to the data/documents and locations where trial activities are carried out (e.g., Laboratories, rooms and hospital pharmacy).

11.3 Data Management

11.3.1 Data Documentation

The clinical report forms are designed for recording assessments by different investigators and they provide accurate advice on definitions of terms. The sponsor or designee will explain in detail how to complete the eCRFs to people involved in data entry.

The data recorded in the eCRFs during the study will be documented under a subject number and the subject will only be identifiable by their subject number. If, as an exception, it is necessary to identify a subject for legal or safety reasons, both the sponsor (including CRO staff) and the investigator are required to maintain the confidentiality of this information.

As a general rule, all information in the eCRF should be traceable to the subject's original documents on file. As a minimum the following information must be available as original data in the patient's medical record kept by the researcher:

- Compliance of the patient to participate in this study (study identified by study number, product under investigation, randomization number), history
- Records of diseases/treatments and concomitant medication, dates of visits,
- Use of study medication, records of adverse events,

- Reasons for premature discontinuation, as appropriate,

All data entered in the eCRF requires that an electronic or written record be defined as original data.

eCRFs are to be filled in immediately after each examination. The investigator will give a reasonable explanation for any missing data. The investigator will sign completed eCRFs to confirm reliability and truthfulness of data.

If the investigator authorizes other people to enter data into the eCRF, this delegation must be documented with the names, positions, signatures and initials of these people.

11.3.2 Data processing

All data will be entered in the eCRF (and corresponding source documents) by investigator or designee according to pre-defined instructions in the Data Entry Manual. Data entry will be performed on an ongoing basis as subjects perform their visits.

■ Electronic Data Capture system (Trial Master) will be used in this study. The EDC system will maintain an audit trail that will document changes together with date and user in the database after the data entry has started.

Laboratories and vendors data will be entered by study staff in the eCRF unless elsewhere specified, in which case electronic files will be uploaded into patients eCRF, as explained in the relevant manuals and detailed in the Data Transfer Specification.

11.3.3 Coding

The following dictionaries should be used for coding:

- Medical history: MedDRA
- Adverse events: MedDRA
- Concomitant medication: WHO-DD (ATC)

11.3.4 Data cleaning

During the initiation phase of the study, a Data Management Plan (DMP) will be developed which will describe in detail how data will be managed.

Automatic checks defined in the Data Validation Plan (DVP) will be generated by the system. Manual queries will also be created, if needed. Investigator or designated site staff will be required to respond to the checks and queries and confirm or correct the data. Query Management will be detailed in the DMP.

11.3.5 Missing and false data

All missing or false data will be investigated. If the investigator cannot provide a reasonable explanation, then the data shall be treated as unresolved queries. All data from the eCRF will be exported into SAS datasets and will be considered for analysis as specified in the statistical analysis plan.

11.3.6 Closing the database

After the study has been completed, the occurrence of any emergency decryption of the code and any violation of the protocol will be determined. Once these actions are completed and the database is declared complete and accurate, it will be closed. Any subsequent changes to the database can only be done through a joint agreement in writing between the Sponsor and [REDACTED].

12 ETHICS

12.1 Institutional Review Board/Ethics Committee

Documented approval from appropriate IRBs/ECs will be obtained for all participating centers/countries prior to study start, according to ICH GCP guidelines, local laws, regulations and organizations. When necessary, an extension, amendment or renewal of the IRBs/ECs approval must be obtained and also forwarded to the sponsor. The IRBs/ECs must supply to the sponsor, upon request, a list of the IRBs/ECs members involved in the vote and a statement to confirm that the IRBs/ECs is organized and operates according to ICH GCP guidelines and applicable laws and regulations.

12.2 Ethical Conduct of the Study

The procedures set out in this protocol, pertaining to the conduct, evaluation, and documentation of this study, are designed to ensure that the sponsor and investigator abide by ICH GCP guidelines. The study will also be carried out in keeping with applicable local law(s) and regulation(s). This may include an audit by the sponsor representatives and/or an inspection by Regulatory Authority representatives at any time. The investigator must agree to the audit or inspection of study-related records by the sponsor representatives and/or Regulatory Authority representatives, and must allow direct access to source documents to the sponsor and/or Regulatory Authority representatives.

Modifications to the study protocol will not be implemented by either the sponsor or the investigator without agreement by both parties. However, the investigator may implement a deviation from, or a change to, the protocol to eliminate an immediate hazard(s) to the study subjects without prior IRB/EC/Sponsor approval/favorable opinion. As soon as possible, the implemented deviation or change, the reasons for it and if appropriate the proposed protocol amendment should be submitted to the IRB/EC/Sponsor. Any deviations from the protocol must be fully explained and documented by the investigator.

No medical waivers for protocol inclusion/exclusion criteria will be allowed by the sponsor, and that in case the need for a change to the protocol is identified, it will be submitted as a protocol amendment to the competent regulatory authority and/or ethics committee as applicable per regulations.

Direct advertising will be used in this study in order to solicit subject participation. Direct advertising includes, but is not necessarily limited to: newspaper, radio, TV, bulletin boards, posters that are intended for candidate subjects. Any advertisement will be submitted for review and approval to the IRB/EC charged with this responsibility to ensure that the information contained in the advertisement is not misleading and that the procedure for recruiting subjects gives adequate protection for the rights and welfare of the subjects.

12.3 Regulatory Authority Approvals/Authorizations

Regulatory Authority approvals/authorizations/ notifications, where required, must be in place and fully documented prior to study start. Study information including contact information for

investigator sites responsible for conducting the study will be posted on a publicly accessible clinical registry (ies) as required by local law.

12.4 Subject Information and Consent

Subject information and ICF will be provided to investigator sites. Prior to the beginning of the study, the investigator must have the IRB/EC written approval/favorable opinion of the written ICF and any other written information to be provided to subjects. The written approval of the IRB/EC together with the approved subject information/ICF must be filed in the study files and a copy of the documents must also be provided to Sponsor by the investigator site.

Written ICF must be obtained from the patient (or legal representative, if applicable) and from a close relative/caregiver before any study specific procedure takes place. Participation in the study and date of ICF given by the subject and by the close relative/caregiver should be documented appropriately in the subject's files. A signed copy of the subject and close relative/caregiver ICFs will be provided to the subject (or subject's authorized representative) and to the close relative/caregiver, respectively.

12.5 Confidentiality

All records identifying the subject will be kept confidential and, to the extent permitted by the applicable laws and/or regulations, will not be made publicly available.

Subject names will not be supplied to the sponsor. Only the subject code number and subject initials will be recorded in the eCRF, and if the subject's name appears on any other document (*i.e.*, pathologist report), it must be removed before a copy of the document is supplied to the sponsor. Study findings stored on a computer will be stored in accordance with local data protection laws. Subjects will be informed in writing that representatives of the sponsor, IRB/EC, or Regulatory Authorities may inspect their medical records and personal health information to verify the information collected, and that all personal information made available for an audit or inspection will be handled in strictest confidence and in accordance with local data protection laws and with the European General Data Protection Regulation (2016/679) (GDPR).

If the results of the study are published, the subject's identity will remain confidential.

The investigator will maintain a list to enable subjects' records to be identified.

12.6 Patient health insurance

During their participation in the study, each subject will be covered by an insurance policy in accordance with the Spanish Medicines Act, which covers any possible risks arising from their participation in the study.

Patients will be informed of the existence of the contract and the obligations that come with it:

- The insured person can only receive other medical treatment during the clinical trial, if the clinical investigator consents to such treatment. Emergency treatment is exempt from this rule.

- The insurer must be informed immediately of any health deterioration that may result from the clinical trial. In case of damages, the subject's signed informed consent form will be presented.

If it is necessary to make an insurance claim, the medical investigator will notify the monitor and sponsor immediately so they can submit the claim to the insurance company.

12.7 Compensation for the subject

By participating in this clinical trial, no additional costs will be incurred. A taxi services and a meal voucher will be available for all participants and caregiver throughout the study. In addition, travel by private car, public transport or taxi will be reimbursed. For private car travel, the amount of fuel used shall be reimbursed; for public transport or taxi, the refund can only be made on presentation of the original receipt. Any additional costs related to participation in this study may be refunded upon presentation of the original receipt. For this, patients should contact the staff responsible for the study during visits.

13 DATA HANDLING AND RECORD KEEPING

13.1 Data Handling

The study data will be recorded and kept current in the eCRF by the site study personnel directly responsible for the information. Entries made in the eCRF must be verifiable against source documents. The data in the eCRF will be monitored at the site by Araclon-Grifols representatives at regular intervals and reviewed for completeness and compared with the source documents. Examples of acceptable source documents include individual subject medical records, prospective information gathered on source documentation worksheets, lab reports and other diagnostics pertinent to this study which are separate from the eCRFs. The listing of types of source documents which will be defined in the source data agreement will be filed in TMF.

All adverse events (AEs) and serious adverse events (SAEs) must be recorded. All SAEs must be recorded on the SAE form. The SAE form must be kept in site records with a copy provided to the designated person as detailed in the study file.

13.2 Record Retention

At study completion, all study data will be transferred to Araclon-Grifols according to ICH GCP guidelines, local laws, regulations, and Araclon-Grifols requirements. The study file and all source data should be retained until notification is given by the sponsor for destruction.

An investigator is required by ICH GCP guidelines to retain the study files. If an investigator moves, withdraws from an investigation or retires, the responsibility for maintaining the records may be transferred to another person (*i.e.*, other investigator). Araclon-Grifols must be notified in writing of the person responsible for record retention and the notification will be retained in the sponsor study file and the investigator site file.

14 FINANCING AND INSURANCE

In the event of subject injury as a direct result of either administration of investigational product or any non-standard of care study procedure, Sponsor will pay for the costs of treatment, provided the subject has followed the instructions given by the study doctor and the illness or injury is not due to the natural progression of any conditions existing before the subject participated in the study. Financial compensation for such things as lost wages, disability, or discomfort due to any research-related injury is not available.

Sponsor shall maintain comprehensive general liability insurance or self-insurance in amounts adequate to cover any damage, demand, claim, loss or liability caused or incurred by Sponsor, or as otherwise required by applicable laws and/or regulations.

15 PUBLICATION POLICY

Institution and the Investigator agree that the first publication shall be made in conjunction with the presentation of a joint, multi-center publication of the study results from all appropriate sites. If such a multi-center publication is not submitted within twelve (12) months after conclusion of the study at all sites or after Araclon-Grifols confirms there will be no joint, multi-center publication, then institution and/or Investigator shall have the right, at their discretion, to publish, either in writing or orally, the results of the study performed under the protocol, subject to the conditions outlined below:

- The results of the study will be reported in the publicly accessible registry(ies).
- Institution and/or Investigator shall furnish Araclon-Grifols with a copy of any proposed publication at least thirty (30) days in advance of the date of submission for publication.
- Within said thirty (30) day period, Araclon-Grifols shall:
 - Review such proposed publication for Confidential Information (other than Study results) and for subject information subject to the Health Insurance Portability and Accountability Act of 1996 (“HIPAA”) and other applicable privacy laws;
 - Review such proposed publication for the unauthorized use of the name, symbols and/or trademarks of Araclon;
 - By written notice to the Investigator, identify with specificity the text or graphics in such proposed publication that Araclon-Grifols contends contains Confidential Information, protected subject information, or the unauthorized use of Araclon or Grifols’ name, symbols and/or trademarks so that the proposed publication may be edited appropriately to remove such text or graphics before publication; and
 - By written request, Araclon-Grifols may delay proposed publications up to sixty (60) days to allow Araclon-Grifols to protect its interests in Araclon-Grifols Inventions described in such publications.
- Institution and/or Investigator shall give Araclon-Grifols the option of receiving an acknowledgment for its sponsorship of the study in all such publications or presentation.

17 APPENDICES

Appendix 1 Definition of adverse reactions

Local reactions:

They are those that occur in the injection area. The appearance of erythema, pruritus and hyperemia in that area is considered as an effect that may be associated with the administration thereof but it's not considered as an adverse reaction. We will consider such case when an induration (wheal) occurs at the site of inoculation of the extract and it has a diameter which is referred below. Regarding to the moment of occurrence of local adverse reaction, we differentiate between:

- Immediate: local adverse reaction that occurs within 30 minutes after extract administration. It is considered that it happens when the largest diameter of the wheal is larger than 5 cm in adult subjects and 3 cm in pediatric subjects.
- Delayed: local adverse reaction that begins 30 minutes after extract administration. It is considered that it happens when the largest diameter of the wheal exceeds 10cm in adult subjects and 7cm in pediatric subjects.

Systemic reactions:

They are those that occur away from the injection site. As in the case of local reactions, we differentiate between immediate or delayed response considering the occurrence within or after the first 30 minutes following extract administration, respectively. The severity of systemic adverse reaction is usually associated with the speed of beginning of the first symptoms of it.

Currently, systemic adverse reactions are ranked in five grades (1-5), depending on their severity, where grade 1 is the least severe and grade 5 is the most sever. Classification in these grades is based on the affected organ and the intensity of the registered clinical manifestations:

- Grade 1: exclusive implication of one of the following systems/organs: skin, conjunctiva, upper respiratory tract, or other (non-specific).
- Grade 2/3: Involvement of more than one of the systems/organs described above or presence of asthma, gastrointestinal involvement or lower respiratory tract (grade 2 with reduced FEV1 baseline of 40% with good response to rescue bronchodilators; grade 3 with a reduction less than 40% without adequate response to the rescue bronchodilators).
- Grade 4: respiratory failure and/or cardiovascular with hypotension (no need to be associated with loss of consciousness).
- Grade 5: death of the subject.

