- Brain MRI at visits:
Part A: V0, V9, V16, V17, V21 and V25
Part B: V1B (only in the absence of a MRI performed within 6 months (± 15 days)), V9B, V16B, V17B, V21B and V22B.
- MRI Central Reader will issue his assessment after every MRI (except V22B). This assessment will be taken into account for subjects' eligibility and /or continuity. In V22B will be performed a MRI to identify any long-term safety issue.
- Amyloid-PET evaluation at visits V0, V21 and V25 (Part A) and V21B (Part B).

CSF collection for the following analysis at

Part A: V1, V21 and at visit V25. Part B: V21B

- Total proteins
- Glucose
- Albumin
- Assessment of biomarkers (A β 42, tau, P-tau, neurogranin, neurofilament light and other A β peptide species)
- Assessment of anti-A β antibodies

Treatment:

- Vaccination (at visits V1, V4, V7, V10, V13 and V18 [Part A] and V1B, V4B, V7B, V10B, V13B and V18B [Part B])

Medical History (at all visits):

- Relevant past and concomitant diseases
- Adverse events
- Concomitant medication

Statistical Methods:*Part A:*Primary Safety Analysis:

The primary safety variable is the frequency (%) of Adverse Events (AEs) over the course of the study. The primary safety endpoint will be analyzed descriptively in the Safety population.

The hypothesis for the primary endpoint for safety is that ABvac40 will be safe for human administration, according to the observed pattern of AEs.

The trial will be considered satisfactory if the pattern of AEs (overall or grouped as neurological, psychiatric or cardiovascular) is consistent with a good safety and tolerability profile of ABvac40 for human administration at the final of the study.

For this primary safety analysis, the amyloid-PET negative and the amyloid-PET positive subjects will be pooled together.

Primary Efficacy Analysis (immunogenicity):

The primary efficacy variable is the maximal increment of specific anti- $\text{A}\beta$ 40 antibody signal (antibody titers estimated by ELISA [signal OD values]) in each subject with regard to the pre-treatment visit (either V0 or V1). For this primary efficacy analysis, the amyloid-PET negative and the amyloid-PET positive subjects will be pooled together.

The trial will be considered successfully confirmatory regarding efficacy (immunogenicity) of ABvac40 if the average maximal increment ($M\Delta$) of anti- $\text{A}\beta$ 40 antibody signal (OD in ELISA) in the verum group is >0 OD than the average $M\Delta$ in the placebo group.

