8.3.3 Adverse Event Definitions

8.3.3.1 Adverse Events

An AE is defined as any untoward medical occurrence in a subject or clinical investigation subject administered a medicinal product or study treatment and which does not necessarily have a causal relationship with this administration. An AE can therefore be any unfavorable and unintended sign (including any abnormal laboratory finding, for example), symptom, or disease temporally associated with the use of a medicinal product, whether or not considered related to the medicinal product.

The frequency of adverse events should be investigated using indirect questions at each study visit (e.g., How are you today? How do you feel?). Adverse events can also be detected when the patient directly and spontaneously reports them during a visit or between visits or by physical examination, blood test and other assessments. Abnormal laboratory parameters are only considered as an adverse event if the researcher classifies them as "clinically significant".

Alzheimer's Disease clinical signs or symptoms and pathological laboratory parameters are not considered adverse events if already present in the first assessment, except when deterioration or increase in frequency is observed.

All adverse events will be documented in a specific form for adverse events. The documentation includes the following information:

- Duration (start and end date),
- Intensity (mild, moderate, severe),
- Possible causal relationship with study treatment (related or not),
- Action taken (no measure taken, adjust dose/temporarily stop study drug, permanently discontinue study drug, administer concomitant medication, provided a nonpharmacological therapy, brief or prolonged hospitalization)
- Assessment of outcome (full recovery, improvement, unchanged, deterioration),
- Meet any of the severity criteria.

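### Protocol Appendix 1 labels most local reactions as not adverse reactions, against Section 8.3.3.2; related-event tables could understate local reactogenicity

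*Protocol*

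**What the plan says.** Protocol Appendix 1 deals with local reactions in two steps. Erythema, pruritus and hyperaemia in the injection area are set aside: the appendix grants that they may be linked with the injection, yet they are "not considered as an adverse reaction. We will consider such case when an induration (wheal) occurs at the site of inoculation". An induration can qualify, but only by size. For an immediate reaction, "It is considered that it happens when the largest diameter of the wheal is larger than 5 cm in adult subjects"; for a delayed one the test is that "the largest diameter of the wheal exceeds 10cm in adult subjects". The appendix gives paediatric limits as well and calls the injected product an *extract*.

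The body of the protocol defines its terms more widely. Under Section 8.3.3.1, "An AE can therefore be any unfavorable and unintended sign", whether or not it is thought related. Under Section 8.3.3.2, a suspected adverse reaction is a noxious and unintended response to the product where a causal link is at least reasonably possible. Section 8.3.4 sets causality by the same test. None of these sections excludes a sign or sets a diameter.

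On the outcome, the synopsis states: "The primary safety variable is the frequency (%) of Adverse Events (AEs) over the course of the study". Section 9.1.3.1 and SAP Section 7.2.1 also tabulate AEs by relationship to study medication, or by maximum causality.

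**The concern.** Appendix 1 accepts a possible link to the injection and then withholds the label that Section 8.3.3.2 attaches to such a link. It is also in use. Section 8.3.10.2 refers to it for assessing reactions to the vaccine, and no other passage defines a local reaction.

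Local reactions are a natural part of the tolerability profile of an adjuvanted subcutaneous injection given six times in Part A. The primary safety criterion is descriptive: the AE pattern must look consistent with good safety and tolerability. Absolute rates and attribution therefore carry the conclusion. If local signs are coded unrelated because the appendix says they are not reactions, or are never carried to the AE page, the related-event tables will show a cleaner local profile than the patients had. Practice could also differ between sites.

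**Working it through.** **The plan's own figure.** Section 9.2 sizes the active arm to see at least one case of an AE with a 5% rate, with probability of at least 95%. The rule of three gives 3/0.05 = 60. Exactly, 1 − 0.95^60 = 0.954. The figure reproduces, but it assumes that every case is recorded.

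**The definitions side by side, for a delayed 8 cm induration or for redness after injection.**
- Section 8.3.3.1: an AE, since no causality or size is required.
- Section 8.3.3.2: a suspected adverse reaction if noxious, unintended and reasonably possibly caused by the product.
- Section 8.3.4: related or not, judged on timing, known response pattern, alternative explanations, and dechallenge or rechallenge.
- Appendix 1: not an adverse reaction, although a link with administration of the product is conceded for redness.

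The conflict is between the second and fourth lines, with strain against the third. The first line is untouched.

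**Where a local sign can go.**
- To the AE page, coded related: it appears in every planned table.
- To the AE page, coded unrelated because of Appendix 1: it stays in the all-TEAE tables but leaves the related-TEAE counts, and it is shown as unrelated in the causality tables.
- Only to the eCRF item for vaccine reactions, which Protocol Sections 4.9.1.2 and 4.9.2 list apart from adverse events at safety calls and face-to-face safety visits: it has no planned summary. Protocol Section 9.1.3 and SAP Section 7 tabulate AEs and give no table of this item. No text says how an entry there reaches the AE page.

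**Bounds on the related-event count.** The documents give no local-reaction rate, so this is illustration only. Let r be the share of patients with a local reaction and f the share of those who drop out of the related count. Patients lost per arm = 60 × r × f.
- f = 0: 0 patients, whatever r is.
- f = 1, r = 10%: 60 × 0.10 = 6.
- f = 1, r = 40%: 60 × 0.40 = 24.

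The upper figures also assume that none of these patients has another related AE. At full dosing each arm has 6 × 60 = 360 Part A injections; with the planned dropout of about 40% there would be fewer.

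**Effect on detection.** Suppose an event with a true 5% rate is captured with probability q in each affected patient (recorded as an AE or, for the causality tables, recorded and coded related). The chance of at least one case in 60 is 1 − (1 − 0.05q)^60.

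| q | chance |
|---|---|
| 1 | 95.4% |
| 0.9 | 93.7% |
| 0.75 | 89.9% |
| 0.5 | 78.1% |
| 0.25 | 53.0% |
| 0.1 | 26.0% |

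The values of q are assumed. If the recording and causality rules in the body of the protocol are followed, q = 1.

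**Between arms.** Both arms receive the aluminium hydroxide vehicle (Section 4.4.1), so vehicle-driven reactions could be lost in both. If the same share f is lost in each arm, a true difference pA − pP is seen as (1 − f)(pA − pP). The comparison with placebo would not expose the loss and would shrink any real excess.

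**The case against.** A reader might infer that Appendix 1 contradicts the AE definition, that sites will therefore not record these signs, and that the primary AE rate is biased. The documents do not support this. The appendix defines adverse reactions, not adverse events, and the primary variable is the AE rate. No passage makes the appendix a filter for AE entry, and the recording rules point the other way:
- Sections 8.2.1 and 8.3.8 require all AEs to be recorded.
- Section 6.1 has the injection site inspected after each dose.
- Section 8.2.4 turns new examination findings after baseline into AEs, and the examination covers skin.
- Section 8.2.7 words local reactions in the diary as one kind of AE and has the diary transcribed to the eCRF.

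All of that stands.

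It can also be said that causality belongs to Section 8.3.4, that conceding a possible association favours coding these signs as related, and that an event coded unrelated still counts in the all-TEAE tables. This is right, and it limits the consequence. It does not remove the conflict: an investigator told that a sign is not an adverse reaction has a written reason to code it unrelated.

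Finally, mild redness may not be noxious, which would soften the clash with Section 8.3.3.2. But that section leaves this to judgement, whereas the appendix excludes by rule, up to and including a 10 cm delayed induration.

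**Conclusion.** The point holds as a conflict between Appendix 1 and Section 8.3.3.2, in tension with 8.3.4, with a possible effect on the related-TEAE and causality tables and on anything left only in the vaccine-reaction item. The direction, if there is an effect, is to understate local reactogenicity and so overstate tolerability, in both arms. The size cannot be derived from the documents. Zero is possible; 6–24 patients per arm is a ceiling that rests on an assumed 10–40% reaction rate and complete loss. An effect on the primary AE rate is not established and would require sites to use the appendix as an entry filter, which nothing tells them to do. The *extract* and paediatric wording does not fit a vaccine trial in patients aged 55–80 and suggests text that was not adapted to this trial; that is an inference. The correction is worth making because it is cheap and bears on how the tolerability objective is read.

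**What to change.** 1. Reconcile Appendix 1 with Sections 8.3.3.1, 8.3.3.2 and 8.3.4. State that it limits neither AE recording nor causality assessment, and that local signs of any size are entered as AEs. Keep wheal diameter as a descriptive field.
2. Remove the *extract* and paediatric wording.
3. Add a SAP table of the local-reaction eCRF item by treatment group, and reconcile that item with the AE page before database lock. For data already collected, this can recover signs held in the item or in the diaries, but not signs that were never written down.
4. Protocol Section 2.6 and SAP Section 2.3 make Part B entry depend on the absence of a drug reaction in Part A. Whether injection-site redness is such a reaction depends on which definition is read. Those passages must be reconciled with the definition that is kept; this review does not say which entry rule is right.

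The cost is a wording change, one table and one data reconciliation. The reported related-AE rate may rise somewhat in both arms.
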